#### 3.2.3.4 Lung function and bronchial hyper-responsiveness

The change from baseline to Week 12 (Visit 9) will be calculated as described in Section 3.1.2 for the following exploratory endpoints:

- FEV1 (Pre-BD and Post-BD)
- FVC (Pre-BD and Post-BD)
- FEF25-75% (Pre-BD and Post-BD)
- AHR PD20, AHR PC20

 $FEV_1$ , FVC and  $FEF_{25-75\%}$  will be determined by spirometry. To ensure quality control all spirometries are reviewed to ensure that they meet ATS/ERS criteria for acceptability. Only those spirometry tracings determined to be acceptable or borderline will be used to determine FEV1, FVC and FEF25-75\%, based on the best measurement selected by ERT per spirogram. Section 5.1.8 of the CSP contains further details of the spirometry recordings.

The percentage change from baseline to Week 12 (Visit 9) described in Section 3.1.2 will also be calculated for AHR PD20/ AHR PC20 as a supportive variable.

#### 3.2.3.5 Asthma Exacerbations

For the purpose of the study, an asthma exacerbation will be defined as a worsening of asthma that leads to any of the following:

- A temporary bolus/burst of systemic corticosteroids for at least 3 days to treat symptoms of asthma worsening; a single depo-injectable dose of corticosteroids will be considered equivalent to a 3-day bolus/burst of systemic corticosteroids
- An emergency room (ER) or urgent care (UC) visit due to asthma that required systemic corticosteroids (as per the above)

• An in-patient hospitalization (defined as admission to an inpatient facility and/or evaluation and treatment in a healthcare facility for  $\geq 24$  hours) due to asthma

Worsening of asthma is defined as new or increased symptoms and/or signs (examination or lung function) that can be either concerning to the subject (subject-driven) or related to an asthma daily diary alert (diary-driven). Baseline values for Asthma Daily Diary variable will be the average of all the daily records within the Visit 1 and Visit 2.

The eDiary will be programmed to alert both the subject and study centre when certain prespecified worsening thresholds are crossed.

Events that are not supported by any objective assessment will be deemed not to be a protocol-defined exacerbation.

In order to calculate the number of exacerbations experienced by a subject during the 12-week treatment period the following rule will be applied:

- The start of an exacerbation is defined as the start date of systemic corticosteroids, ER or UC visits requiring systemic steroids or hospital admissions due to asthma, whichever occurs earlier.
- The end date is defined as the last day of systemic corticosteroids or ER or UC visit or hospital discharge, whichever occurs later.

An asthma exacerbation that occurs  $\leq$  7 days since the last dose of systemic steroids, prescribed for a prior exacerbation, will be counted as the same exacerbation event.

For the production of summary statistics, the annual exacerbation rate per subject is calculated, and standardized according per a 52-week period according to the formula described below.

Annual Exacerbation Rate = No. of Exacerbations\*365.25 / (last Follow-up date – Date of randomization + 1).

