# 1.2 Study design

This multicentre, randomized, double-blind, parallel group, placebo-controlled, phase 2 study will evaluate the effect of a 300 mg dose of tralokinumab administered subcutaneously (SC) every 2 weeks on airway inflammation in adults with asthma inadequately controlled on ICS ( $\geq$  250 mcg fluticasone dry powder formulation equivalents total daily dose) with or without other controllers.

The subjects (males and females, 18 to 75 years of age at screening inclusive) will be randomized to 12-Week treatment with tralokinumab or placebo (1:1).

Approximately 80 subjects will be randomized.

After initial enrolment and confirmation of entry criteria, subjects will proceed to a run-in period of 4 weeks during which their suitability for randomisation will be confirmed. Subjects who meet the eligibility criteria at visit 3c will be randomized to a 12-week treatment period. The subjects' currently prescribed ICS and additional asthma controller medication will remain unchanged during the run-in and treatment period.

EOT (End of Treatment) visit will be at Week 12 (Visit 9). Post-treatment follow-up period for all subjects will be for 14 Weeks after the EOT visit with a telephonic follow-up (FU) 1 visit (Visit 10, Week 16). There will be an on-site FU 2 visit (Visit 11, Week 26) for WOCBP only, to also ascertain their pregnancy status. For all other subjects this will be a telephonic FU 2 visit.

A graphical view of the study is shown in Figure 1.

# Study flow chart Figure 1

Follow-up Week 16, 26 
End of Treatment Week 12
12-week double-blind randomized Treatment period Week 0 up to Week 10
Randomization Week 0
Enrolment/ Run-in Week -4, -2, -1

1. Due to multiplicity of assessments, Visit 3 is spread over 3 visits, Visit 3a, 3b and 3c. Visit 3c being the randomization visit when IP is administered for the first time. 2. WOBCP will have an on-site follow-up visit at Week 26 to also ascertain their pregnancy status.

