#### 4. ANALYSIS METHODS

#### 4.1 General principles

The analysis of the study endpoints will include all data captured during the 12-week doubleblind treatment period. This includes data regardless of whether IP was prematurely discontinued or delayed, and/or irrespective of protocol adherence, unless the subject withdraws consent to study participation.
Only exacerbations confirmed to meet the protocol definition (CSP Section 5.1.12) will be included in exploratory summaries. This includes only exacerbations that started on or after the date of randomisation, and those that are defined as a worsening of asthma that leads in at least one of the three criteria detailed in protocol Section 5.1.12 being fulfilled. This will include exacerbations where the eCRF exacerbation records a new/worsened symptom, requiring systemic corticosteroid intervention or hospitalization.

A summary table which counts subjects who have been incorrectly randomized and who received incorrect treatment will be presented.

Summary data will be presented in tabular format by treatment. Categorical data will be summarized by the number and percentage of subjects in each category. Continuous variables for parametric data will be summarized by descriptive statistics including N, mean, standard deviation (SD), geometric mean, SD of log values, median, minimum and maximum. All data will be listed. Data listings will be sorted by treatment and subject number.

Measures of location (mean, geometric mean, median, minimum and maximum) will be reported to the same degree of precision as the raw data unless otherwise stated. Measures of spread (SD) will be reported to one further degree of precision.

Continuous descriptive statistics for the percent and absolute change from baseline will summarize N, mean, SD, median, minimum and maximum and will be based on raw data. Continuous descriptive statistics for the ratio will summarize N, geometric mean and SD of log values and will be based on log-transformed data. Primary and secondary efficacy variables will summarise the ratio, absolute and percent change, exploratory efficacy variables will summarise absolute and percent change, and non-efficacy summary statistics on the change from baseline will only present the absolute change.

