# 4.2.6.3 Exacerbation

Exacerbations will be listed only.

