- permanent discontinuation of study drug.

Severe infections will be summarized by MedDRA high level group term, high level term and preferred term by treatment group for the treatment period and study period.

The rate of AEs per person-years at risk, calculated as (number of subjects reporting AE)/(total time at risk of AE), will also be reported. Rates will typically be expressed in terms of events per 100 subject-years. Total time at risk will be defined as the date of last visit in the 12-week treatment period – date of randomization +1.

Separate listings of subjects with AEs, SAEs, death due to AE, discontinuations due to AEs, or severe infections will be presented.

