# 6. CHANGES OF ANALYSIS FROM PROTOCOL

A number of clarifications and minor corrections have been made and are listed below:

- Section 3.4.3/4.2.9.2: due to the way the data is collected on the eCRF, the urinalysis categories have been updated to negative, trace or positive.
- The presentation of asthma exacerbations is not detailed in the protocol. This has been added as an exploratory variable (Section 1.1.4) and some text detailing summaries that will be provided have been included In addition, a start and end date definition of an exacerbation has also been added.
- Section 3.3.1.5: Categorisation of Improved/ No Change/ Deterioration has be relabelled as ACQ-6 Response to be distinct from ACQ-6 Responder which is Yes or No.
- Section 1.1.4 p.15: The analysis is now calculate the change from baseline up to Week 12 in fractional exhaled nitric oxide ( $FE_{NO}$ )
- Section 3.1.1: Baseline for Asthma Daily Diary variables will be, for each variable, the average of all the daily records within the 14 days prior to randomization
- Section 3.2.3.1 to Section 3.2.3.3: ratios will also be calculated for sputum, serum, large and small airways remodelling variables
- Section 3.3.1.3: Bi-weekly mean number of nights is expressed as a percentage
- Section 3.4.1 and 4.2.2: increased follow-up period to 20 weeks
- Section 1.1.4 and 3.2.3.2, 3.2.3.3: The three types of change from baseline analyses (absolute, percent, ratio) will be performed for all exploratory endpoints.
- Section 3.2.3.1: Removed analysis of soluble biomarkers, serum biomarker, nasosorption biomarkers, airway epithelial gene expression, airway volume and resistance based on FRI, effect of Tralo on RNA.
- Removed references to sub-sub segmental as team will be combining sub-segmental and sub-sub-segmental analyses together.
- SNOT-20 is coming from RAVE, and not from the e-diary data.
- The change in sputum eosinophils as percentage number of inflammatory cells won't be analysed (this was a supportive secondary outcome measure added in protocol amendment 2).
- MMRM only performed on secondary efficacy; not on efficacy

- Section 2.1.3: The definition of PK analysis set has been updated to include subjects in FAS who received tralokinumab and had blood samples obtained for PK.
- Section 3.4.2: The OAEs have been updated to safety topics of special attention
- Section 4.1: Under general principles, the p-values rounding has been updated from 3 to 4 decimal places (reference CSP section: 8.5).

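### The AE rate counts subjects but is labelled as events and names no AE period; the exacerbation rate has an undefined end date and conflicts with a listing-only plan

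*SAP*

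**What the plan says.** **AE rate.** SAP 4.2.9.1 says a person-time rate of AEs will be reported, "calculated as (number of subjects reporting AE)/(total time at risk of AE", normally shown as events per 100 subject-years. Time at risk runs from randomization to the final visit of the 12-week treatment period. The same section summarises AEs for a treatment period and for a study period, and the rate text names neither. SAP 3.4.1 ends the treatment period for AEs two weeks after the last dose. Protocol 6.3.1 collects AEs up to the FU 2 visit.

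**Exacerbation rate.** SAP 3.2.3.5 introduces its counting rule with "In order to calculate the number of exacerbations experienced by a subject during the 12-week treatment period the following rule will be applied". It continues "For the production of summary statistics, the annual exacerbation rate per subject is calculated" and gives the formula as the number of exacerbations times "365.25 / (last Follow-up date – Date of randomization + 1". Neither document defines that last date. SAP 1.2 uses the term for the phase after treatment: "Post-treatment follow-up period for all subjects will be for 14 Weeks after the EOT visit".

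**Exacerbation reporting.** SAP 4.2.6.3 says "Exacerbations will be listed only". SAP 4.1 says "Only exacerbations confirmed to meet the protocol definition (CSP Section 5.1.12) will be included in exploratory summaries". SAP Section 6 says of exacerbations: "This has been added as an exploratory variable (Section 1.1.4) and some text detailing summaries that will be provided have been included". SAP 1.1.4 contains no exacerbation variable.

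**The concern.** A rate can be interpreted only if numerator, person-time and label refer to the same thing over the same interval. In the AE rate the label and the numerator differ, and one person-time definition could be paired with either of two AE periods. In the exacerbation rate the count is tied to 12 weeks while the person-time ends on a date that a programmer must guess. The SAP also does not settle whether that rate is produced at all. At stake are a mislabelled safety rate and, possibly, an exacerbation rate that is too low. The AE rate is the firmer problem, because the SAP says it will be reported.

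**Working it through.** The documents state no numerical AE or exacerbation rate, so there is no planned figure to reproduce. The check puts the SAP's own target days into its formulas.

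**Inputs.** Target days from SAP Table 1: Week 10 = 71, Week 12 = 85, Week 16 = 113, Week 26 = 183. Doses are at Weeks 0, 2, 4, 6, 8 and 10. Protocol Table 1 gives windows of ±3 days at Visit 8 and ±7 days at Visit 9, with all visits scheduled from randomization. I take the last visit of the 12-week period to be Visit 9.

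**1. AE numerator against label.** Subjects and events agree only if nobody has more than one AE. Illustration (assumed figures): 40 subjects at risk for 85 days each give 40 × 85 / 365.25 = 9.31 subject-years. If 20 subjects have an AE, the SAP formula gives 100 × 20 / 9.31 = 214.9 per 100 subject-years. A true event rate would be 214.9, 376.0 or 644.6 if those 20 subjects had 20, 35 or 60 events.

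**2. AE time at risk against the treatment window.**
- On-schedule completer: the window ends on day 71 + 14 = 85 and time at risk is 85 days. Ratio 1.00.
- Completer at opposite limits of the visit windows: last dose on day 68 to 74, so the window ends on day 82 to 88, with Visit 9 on day 78 to 92. Extremes are 82/92 = 0.89 and 88/78 = 1.13.
- IP stopped after k doses, with attendance to Week 12: the last dose is on day 14(k − 1) + 1 and the window ends on day 14k + 1.

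| Doses received | Window (days) | Window / 85 |
|---|---|---|
| 1 | 15 | 18% |
| 2 | 29 | 34% |
| 3 | 43 | 51% |
| 4 | 57 | 67% |
| 5 | 71 | 84% |

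**3. AE time at risk against the study period.** From randomization to FU 2 is 183 days. Time at risk covers 85/183 = 46% of it. A study-period count of subjects over this denominator would be 183/85 = 2.15 times the figure over the full period.

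**4. Exacerbation rate, one event within 12 weeks.**

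| Meaning of the end date | Rate per year | Relative to Week 12 |
|---|---|---|
| Week 12 | 365.25/85 = 4.30 | 100% |
| Week 16 | 365.25/113 = 3.23 | 85/113 = 75% |
| Week 26 | 365.25/183 = 2.00 | 85/183 = 46% |

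**5. Exacerbation reporting.** Listing only (SAP 4.2.6.3) cannot be followed together with a rate computed for summary statistics (3.2.3.5), exploratory summaries (4.1) and summaries to be provided (Section 6). The Section 6 pointer to 1.1.4 leads to no such variable.

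**The case against.** The strongest reply is that much of this is conditional.

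- **Exacerbations.** If they are only listed, no rate exists and the formula is leftover text. If the date means Week 12, the formula is right. That reading is open: SAP 3.4.5 calls the post-baseline complete physical examinations follow-up, and Protocol Table 1 schedules the only such examination at Visit 9. The formula itself does not repeat the 12-week limit, SAP 4.1 bounds exacerbations only from randomization, and Protocol Table 1 collects them to Visit 11, so a count and a denominator that both run to Week 26 would at least match. All of this stands. The 75% and 46% figures need a 12-week count with a later end date. The counting rule supports that numerator, and SAP 1.2 and Table 1 make that end date plausible, but neither is certain.
- **AE period.** A reader might infer that time at risk fits neither AE period for anyone. It does not go that far: an on-schedule completer has 85 days in both, and window deviations run in either direction. Defining time at risk by the 12-week treatment period also suggests that a treatment-period rate was meant. The 46% coverage therefore describes a rate that the SAP leaves possible but does not specify.
- **Early stoppers.** Protocol 3.9.2 calls for end-of-treatment assessments as soon as possible after withdrawal, so for many such subjects the last treatment-period visit may fall near the last dose. SAP 4.2.1 does plan to tabulate subjects who stop IP and remain in the study, so the case is real, but its frequency is not given.
- **First event.** A reader might also infer that time must stop at each subject's first AE. Subjects with an AE over total exposure is a reproducible summary, computed the same way in both arms. Stopping time is a choice of method, and sizing its effect needs AE proportions and a hazard that the documents do not give.

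The mismatch between subjects and events, the unnamed AE period, the undefined date and the reporting conflict all survive.

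**Conclusion.** Wrong as written, low severity. The AE rate does not measure what its label says. Its person-time is right for on-schedule completers, too long for subjects who stop IP early and attend to Week 12 (counted window 18% to 84% of the denominator), and would cover 46% of the study period if used there. The overall size is unknown, because neither the share of early stoppers nor the number of events per subject is given.

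The exacerbation rate is 75% or 46% of the matched rate only if the end date means Week 16 or Week 26 and a rate is actually produced. The documents do not support saying that it will be understated. They support saying that it could be, and that the listing and summary statements cannot all be followed.

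The results assume target-day visits unless stated. AE counts and percentages are reported separately, and the primary and secondary analyses are unchanged.

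**What to change.** **AE rate (SAP 4.2.9.1).** Name the AE period. For the treatment period, run time at risk from first dose to two weeks after last IP, or to last contact if earlier. For any study-period rate, run it to last contact. Then either label the result as subjects with an AE per 100 subject-years, or count events and keep the present label. Stopping time at the first AE is optional; if it is done, say so.

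**Exacerbations.** Choose one:
- Listing only: delete the rate formula from SAP 3.2.3.5 and bring 3.2.3.5, 4.1 and Section 6 into line with 4.2.6.3.
- Rate reported: end both the count and the person-time at one defined date (the Week 12 visit, or last contact if earlier) and amend 4.2.6.3.

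In either case, correct the Section 6 pointer to 1.1.4.

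**Cost.** SAP wording and denominator code only; no new data.

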#### **3.3** Calculation or derivation of patient reported outcome variables

Patient-reported outcomes data will be captured via an ePRO device. The definition of exploratory outcome variables based on the ePRO are provided in the following sections.

For asthma symptom score, rescue medication use and home PEF, bi-weekly means will be calculated. A bi-weekly mean is calculated as the sum of all non-missing daily measures/scores over 14 sequential days before a visit, up to an including the morning recording on the day of that visit (if appropriate), divided by the number of non-missing daily measures/scores during the same 14 days. Where a total measure/score that encompasses the sum/combination of daytime and night-time diary entries is calculated, the night-time recording for a given day will be the entry recorded the same morning (e.g. if the first IP

administration happens on Day 1, the first total measure/score that can be calculated is for Day 2 and will be the combination of the night-time measure/score recorded on the morning of Day 2 plus the daytime measure/score recorded on the evening of Day 2).

For nights with awakenings due to asthma, the bi-weekly mean will be the percentage of times the subject answered "yes" to 'did your asthma cause you to wake up' and "yes" to 'did you use rescue medication upon awakening'. If more than 7 daily measures/scores (>50%) within a period is missing, then the bi-weekly mean for that period is set to 'missing'.

#### 3.3.1 PRO Exploratory Variables

#### 3.3.1.1 Asthma symptom score

Asthma symptoms during daytime and night-time will be recorded by the subject each evening and morning in the ePRO tool. Symptoms will be recorded using a scale 0-3, where 0 indicates no asthma symptoms. Asthma symptom daytime score (recorded in the evening and referring to the current day), night-time score (recorded in the morning and referring to the night before), and total score will be calculated and presented separately.

The daily asthma symptom total score will be calculated by taking the sum of the daytime and the night-time asthma symptom scores within a day. If a subject is missing a value for either night-time or daytime asthma symptom score on a given day then the total score for that day will be set to missing.

The outcome variable is the bi-weekly mean daily asthma symptom total score. The Week 12 (Visit 9) bi-weekly mean will be the sum of the daily total scores for 14 sequential days up to and including the total score calculated for the day before the Week 12 (Visit 9) visit divided by the number of non-missing daily total scores during the same 14 days.

Bi-weekly means for daytime and night-time scores will also be calculated. The Week 12 (Visit 9) bi-weekly mean daytime score will be the sum of the daytime scores for 14 sequential days up to and including the daytime score entered on the evening before the Week 12 (Visit 9) visit divided by the number of non-missing daytime scores during the same 14 days.

The Week 12 (Visit 9) bi-weekly mean night-time score will be the sum of the night-time scores for 14 sequential days up to and including the night-time score entered on the morning of the Week 12 (Visit 9) visit divided by the number of non-missing night-time scores during the same 14 days.

The number of asthma symptom-free days will be calculated for each subject as the total number of days in the 12week treatment period where the total asthma symptom score is 0. The proportion of asthma symptom-free days will be calculated using the total number of days with completed asthma symptom score diary during the 12week treatment period as the denominator.

#### 3.3.1.2 Rescue medication use

The number of rescue medication inhalations and nebulizer treatments taken will be recorded by the subject in the ePRO twice daily. Daytime use is recorded in the evening and night-time use is recorded in the morning. Inhaler usage will be reported as the number of puffs in a given period whereas nebulizer use will be reported as the number of times.

The number of inhalations of rescue medication and nebulizer treatments captured in the eDiary each day will be calculated per subject. If a subject is missing a value for either night-time or daytime rescue medication on a given day, then the total rescue medication use for that day will be set to missing.

The number of inhalations (puffs) per day will be calculated as follows:

Number of night inhaler puffs + 2x [number of night nebulizer times] + number of day inhaler puffs + 2x [number of day nebulizer times].

Bi-weekly mean number of inhalations (puffs) per day will be calculated as the outcome variable. The Week 12 (Visit 9) bi-weekly mean will be the number of inhalations (puffs) for 14 sequential days up to and including the number of inhalations (puffs) calculated for the day before the Week 12 (Visit 9) visit divided by the number of non-missing daily total scores during the same 14 days.

